#### **11.7.3 Vital Sign Analyses**

Summary statistics will be calculated for measured values and changes from baseline in the supine and orthostatic blood pressure, and supine pulse rate at each scheduled visit.

#### **11.7.4 Electrocardiogram Analyses**

A shift table will be provided for ECG evaluation between baseline and Visit 10.

#### **11.7.5 Physical Finding Analyses**

Summary statistics will be calculated for measured values and changes from baseline in body weight at each scheduled visit. For the evaluation of edema, the results (presence or absence) will be tabulated for each expression site.

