### **3. STUDY DESIGN**

#### **3.1 Overall Plan**

##### **3.1.1 Study Type**

This is an open-label study for treatment of DPNP or PHN in subjects with moderate to severe renal impairment.

Study sites: Approximately 35 study sites in Japan.

Planned sample size: Approximately 35 subjects will be enrolled in the study.

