### **3.2.3 Study Endpoints**

The safety endpoints were selected to evaluate the safety of DS-5565 in subjects with renal impairment. AEs, clinical laboratory evaluations, ECG, and vital sign are commonly evaluated for safety assessment in clinical studies. Body weight was selected to evaluate edema, which is a known adverse reaction of DS-5565.

Assessments by HADS and C-SSRS were selected to evaluate the risk of anxiety, depression, or suicidal tendency. Neurological examination was selected to evaluate gait/station and muscle strength. The efficacy endpoints were selected to evaluate the effect of DS-5565 on pain reduction, sleep interference, and the symptoms of DPNP or PHN.

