### 9.1 Adverse Events

#### 9.1.1 Definition of Adverse Event

An AE is any unfavorable and unintended sign (including an abnormal laboratory value or abnormal vital sign), symptom, or disease that develops after the subject signs the Informed Consent Form (ICF) and up to 7 days after the last dose of study medication (Visit 11), regardless of relationship to the investigational product.

Any symptom that the investigator or sub-investigator considers associated with DPN will be evaluated as an efficacy variable and will not be regarded as an AE. However, if the symptom is considered potentially related to the investigational product, such symptom will be regarded as an AE. If any pre-existing symptom or disease is aggravated during the study period, the aggravation will be reported as an AE, and the date of confirming the aggravation will be considered the date of event onset.

Dizziness, somnolence, edema, and weight increase are currently defined as “significant AEs”. Any other significant AEs to be added will be specified in the statistical analysis plan (SAP).

All antiepileptic drugs carry a risk of increased suicidal behavior and ideation. Furthermore, increased hepatic transaminases have been observed in the DS-5565 development program. Therefore, the following “suicidal behavior and ideation” and “liver enzyme elevations/liver dysfunction” will be treated as AEs of special interest.

- Increase in ALT or AST  $\geq 5 \times$  ULN
- ALT or AST rises to  $\geq 3 \times$  ULN and persists for more than 2 weeks
- Concurrent increases in ALT or AST  $\geq 3 \times$  ULN and T-Bil  $\geq 2 \times$  ULN
- ALT or AST  $\geq 3 \times$  ULN associated with a clinical presentation suggestive of liver injury (ie, including the appearance of fatigue, nausea, vomiting, jaundice, right upper quadrant pain or tenderness, fever, rash, and/or eosinophilia)
- Serious hepatobiliary AE
- Severe hepatobiliary AE

- Hepatobiliary AE leading to discontinuation
- Any transaminase elevation associated with a clinical presentation suggestive of liver injury
- An elevation of ALT or AST  $\geq 3 \times$  ULN (without clinical presentation suggestive of liver injury)
- AE related to suicide (if there are any “yes” responses to any of the questions in the C-SSRS)

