#### **9.1.2 Items to Be Investigated Concerning Adverse Events**

If an AE develops during the clinical study, the items in Table 9-1 will be investigated and the results will be recorded. The subject should be questioned in a general way, without asking about the occurrence of any specific symptoms.

Table 9-1: Items to be Investigated for Adverse Event

Items reviewed	Content of review	
Content of AE	Name of AE, date of onset	
Action taken regarding the investigational product	None	No change in investigational product dosage was made.
	Discontinued	The investigational product was permanently stopped.
	Permanently	
	Interrupted	The investigational product was temporarily stopped.
Outcome	Dose Reduced	The dosage of the investigational products was reduced.
	Classification of outcome, date of outcome assessment, date of resolution	
	Classification of outcome	
 
Recovered/Resolved
 

	Recovered/Resolved with Sequelae	
 
The subject fully recovered from the AE, with no residual effects observed.
 
The residual effects of the AE are still present and observable.
 
Identify sequelae/residual effects.
 

Severity	Not Recovered/Not Resolved	
 
Identify sequelae/residual effects.
 
The AE itself is still present and observable.
 

	Recovering/Resolving	
 
The AE was almost fully resolved, and the subject recovered to near-baseline status.
 

	Unknown	
 
No information and the outcome was unknown.
 

	Fatal	
Seriousness	Mild	Awareness of sign or symptom, but easily tolerated, ie, does not interfere with subject's usual function
	Moderate	Discomfort enough to cause interference with usual activity
	Severe	Incapacitating with inability to work or do usual activity, ie, interferes significantly with subject's usual function
Definition of SAE	Serious (according to the following definition of SAEs) / Not serious	
	
 
1. Results in death
 
2. Life-threatening
 
3. Requires inpatient hospitalization or prolongation of existing hospitalization
 
4. Results in persistent or significant disability/incapacity
 
5. A congenital anomaly/birth defect
 
6. An important medical event
 
	

Table 9-1: Items to be Investigated for Adverse Event (cont.)

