## **9.7 Physical Findings**

### **9.7.1 Body Height and Weight**

At Screening (Visit 1), body height will be measured. Body weight will be measured at each visit. Results will be recorded in the CRF.

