### **11.2 General Statistical Considerations**

The statistical package SAS® (Version 9.2 or higher) will be used to produce tables, figures, and listings.

Safety analysis set will be used for all safety and efficacy analyses and PK analysis set will be for all PK analyses. All analyses will be conducted by CrCL group (ie, moderate and severe renal function impaired patients group).

Missing weekly ADPS value will be imputed based on "nonfuture dependence" model using the pattern mixture approach under the missing not at random (MNAR) mechanism so that bad outcomes (greater weekly ADPS value) can be attributed to subjects who discontinued the trial before Week 14. Detail will be at Section 11.5.2.1 and in the SAP.

Raw data will be presented to the exact precision at which they were collected. For summary statistics, means and medians will be displayed to one more decimal place than was determined for raw data, dispersion statistics will have two more decimal places, and the minimum and maximum will be displayed to the same number of decimal places as the raw data.

Quantitative data will be tabulated with descriptive summary statistics: arithmetic mean, standard deviation (SD), median, minimum and maximum values, and number of observations. For categorical data, frequency tables will be provided.

Analysis for the change from baseline, including the shift table, will be conducted for the subjects who have an available baseline value and at least 1 post-randomization value.

PK analysis will be detailed in the PK analysis plan (PAP).

A detailed SAP and PAP describing the methodology to be used in the final analysis will be prepared before data unblinding. A change in the planned statistical analysis will require a protocol amendment only if it substantively alters the principal features of the protocol. Any deviations from the planned statistical analyses in the protocol will be fully described in the SAP and PAP.

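### Weight increase is a named significant AE, but no planned table counts how many subjects gained a marked amount of weight

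*Combined protocol and SAP*

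**What the plan says.** - Section 9.1.1 on the named events: "Dizziness, somnolence, edema, and weight increase are currently defined as" significant AEs. No amount or percentage of gain is attached to weight increase there or anywhere else in the protocol.
- To be counted, a weight increase must meet the general definition: "An AE is any unfavorable and unintended sign (including an abnormal laboratory value or abnormal vital sign), symptom, or disease" (9.1.1). Section 9.1.2 keeps elicitation open: "The subject should be questioned in a general way, without asking about the occurrence of any specific symptoms".
- Section 11.7.1 counts subjects with significant TEAEs and significant ADRs, by CrCL group and for all DS-5565 subjects together.
- Section 9.7.1: "Body weight will be measured at each visit". Table 17-1 agrees, from Visit 1 to Visit 11 and at early termination.
- Section 3.2.3 gives the reason: "Body weight was selected to evaluate edema, which is a known adverse reaction of DS-5565".
- Section 11.7.5 gives the only analysis of those weights: "Summary statistics will be calculated for measured values and changes from baseline in body weight at each scheduled visit". Section 11.2 fixes the content: "Quantitative data will be tabulated with descriptive summary statistics: arithmetic mean, standard deviation (SD), median, minimum and maximum values, and number of observations".
- The dedicated edema evaluation is done at Visits 1 and 10 (9.7.3), and at early termination under Table 17-1. Section 11.7.5 tabulates its result as present or absent by body site.
- Section 11.7.2, by contrast, plans shift tables for laboratory values and subject counts against guideline criteria for ALT, AST, T-Bil and ALP.

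**The concern.** Safety and tolerability form the primary endpoint, and weight increase is one of four events singled out within it. A reader of the study report will want to know how many subjects gained a marked amount of weight. Two planned outputs bear on this, and neither answers it.

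The AE table gives a number of subjects, but a gain enters it only when an investigator reports it, and nothing says how large a gain qualifies. The weight table uses every measurement, but reduces them to group statistics at each visit. Its maximum shows one subject's gain at one visit. It does not show how many others came close, or whether the maxima at successive visits belong to the same subject.

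An objective measurement, taken at every visit and tied to a named event, is therefore never turned into a per-subject count.

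**Working it through.** **The plan's own figure.** Section 11.11 asks for 30 subjects to see at least one event with 95% probability at a 10% rate. The formula is 1 − (1 − p)^n:

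- n = 28: 1 − 0.9^28 = 0.948
- n = 29: 1 − 0.9^29 = 0.953
- n = 30: 1 − 0.9^30 = 0.958

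The stated 30 is sound (exact minimum 29). It concerns dizziness and somnolence, not weight. The protocol contains no figure for weight gain: no rate, SD or cut-off. Everything below is illustration on assumed inputs.

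**1. Does the mean change reveal the count?** Assume 35 subjects, normally distributed change and a mean gain of 1% of baseline. The expected number at or above a cut-off c is 35 × [1 − Φ((c − 1)/SD)].

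| SD of change | c = 5% | c = 7% |
|---|---|---|
| 2% | 0.8 | 0.0 |
| 3% | 3.2 | 0.8 |
| 4% | 5.6 | 2.3 |
| 5% | 7.4 | 4.0 |

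The mean is the same throughout, and the count varies several-fold. The planned SD, minimum and maximum give a rough indication, but no count.

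**2. How far does one large gain move the mean?** Assume one 5 kg gain and an SD of change of 1 to 1.5 kg. The shift is 5/n and the standard error is SD/√n.

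- n = 10: shift 0.5 kg, SE 0.32 to 0.47 kg
- n = 25: shift 0.2 kg, SE 0.20 to 0.30 kg

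The shift is about the size of the standard error, so the mean hides such a subject. The planned maximum would show that subject.

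**3. What would the AE count show?** Assume each of 35 subjects has a 10% chance of a marked gain, and each such gain is reported with probability r. The reported rate is 0.10r, and the chance that none is recorded is (1 − 0.10r)^35.

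| r | Reported rate | Chance of none recorded |
|---|---|---|
| 0.3 | 3% | 0.97^35 = 34% |
| 0.6 | 6% | 0.94^35 = 12% |
| 0.9 | 9% | 0.91^35 = 4% |
| 1.0 (benchmark) | 10% | 0.90^35 = 2.5% |

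The last row is the chance of no event with complete reporting. At r = 0.9 nearly all of the 4% is sampling; incomplete reporting matters mainly in the first two rows.

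**4. Precision of the proposed count.** Exact 95% intervals are 0 to 10.0% for 0/35, 1.8 to 23.1% for 3/35, and 8.4 to 36.9% for 7/35. The count would be descriptive and wide, like every other incidence in a study of this size.

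**The case against.** **Investigator reporting is how AE tables normally work.** Dizziness and somnolence are counted in the same way. That is true, but weight differs in that a measurement exists for each subject at each visit and could support a second, standardised count.

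**Edema is covered elsewhere.** It is evaluated directly and tabulated, and physical examinations at the other visits include the extremities (9.7.2). This narrows the gap. But the dedicated evaluation is not scheduled between Visits 1 and 10 except at early termination, and weight increase is a significant AE in its own right.

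**The detail may sit in the SAP.** Section 11.2 announces a detailed SAP, and cut-offs are ordinary SAP content. That document is not in the text available here, so the point is limited to what the protocol specifies.

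**Nothing is lost.** The count can be produced at any time from collected weights, and no test or decision rule depends on it. This stands and limits the weight of the point. But in an open-label study, a cut-off chosen after the weights have been seen is less credible than one fixed beforehand.

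**Stronger readings that a reader might infer:**

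- *That weight gain goes unmeasured.* It does not. What is missing is a tabulation.
- *That the spread of sites makes the AE count worse.* Section 3.1.1 has "Study sites: Approximately 35 study sites in Japan" for about 35 subjects, roughly one each. If sites differ in how readily they report and each contributes one subject, the total behaves as though all sites used the average reporting probability. A few investigators with many subjects each would be the worse case.
- *That the AE rate shows reporting habits instead of drug effect.* The documents give no reporting rate, so this cannot be shown. In a single-arm study, a threshold count would not isolate drug effect either.

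**Conclusion.** The point holds in a limited form. The protocol names weight increase as a significant AE and measures weight throughout, yet plans no threshold-based count of subjects who gained weight. The incidence of this event rests on AE reporting with no stated amount of gain, and the group summaries cannot supply the missing number.

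This affects one component of the primary safety description. It does not affect sample size, conduct or any formal inference. Its numerical size cannot be derived from the documents: the 34%, 12% and 4% rest on an assumed 10% rate and assumed reporting probabilities, and must be read against the 2.5% that would arise with complete reporting. The conclusion itself needs none of these figures, since it follows from sections 9.1.1, 9.1.2, 11.2, 11.7.1 and 11.7.5 read together. It is a worthwhile, inexpensive improvement, subject to what the announced SAP may already contain.

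**What to change.** In section 11.7.5, or in the announced SAP, before the weight data are reviewed:

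- Add the number and percentage of subjects whose highest weight after the first dose exceeds the Visit 2 weight by percentage cut-offs that the sponsor chooses and states in advance. Name Visit 2 as the baseline, because weight is also taken at Visit 1.
- Report this by CrCL group and overall. Section 11.7.1 specifies an all-subject column for AEs, but 11.7.5 does not specify one for weight.
- Cross-tabulate these subjects by whether a weight-increase or edema AE was reported, so that agreement between the two sources is visible.
- Keep the planned summary statistics. Exact 95% intervals beside the percentages would show how wide the uncertainty is.

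The cost is one extra table from weights already collected and a sentence or two of text, with no new visits, subjects or measurements. The drawback for the sponsor is that the count may look less favourable than the AE rate.

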#### **11.7.6 Columbia-Suicide Severity Rating Scale**

The data collected from C-SSRS will be tabulated.

#### **11.7.7 Hospital Anxiety and Depression Scale**

The subscales of anxiety and depression for HADS will be summarized at each scheduled visit.

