### **1.3 Risks and Benefits for Study Subjects**

The clinical efficacy of DS-5565 has been established in 2 Phase 2, multi-center, randomized, double-blind, placebo-, and active-comparator controlled adaptive studies in subjects with DPNP. In DS5565-A-U201 conducted in the US, DS-5565 15 mg QD, 10 mg BID, and 15 mg BID treatment groups demonstrated statistically significant mean reductions in ADPS from baseline to end-of-treatment compared to placebo. In DS5565-A-J202 conducted in Asian countries, DS-5565, 5, 10, and 15 mg BID showed numerically mean reductions in ADPS, although the reductions were not statistically significant. The results were supportive of the US study. These data provide proof-of-concept for DS-5565 as a treatment for DPNP and suggest that DS-5565 may have utility in other chronic pain conditions, such as PHN and FM.

Anticipated risks of DS-5565 include the occurrence of adverse reactions related to CNS depression, such as dizziness and somnolence, as well as peripheral edema. Other notable TEAEs that have been observed in Phase 1 and Phase 2 studies include elevations of hepatic transaminases and suicide/suicidal ideation, both of which are carefully monitored and assessed as AESI in the ongoing Phase 3 DPNP, PHN, and FM programs. Ongoing monitoring of the Phase 3 program has identified no new safety concerns. For the approved  $\alpha_2\delta$  ligands, in addition to dizziness, somnolence, and peripheral edema, certain adverse reactions requiring caution have also been reported, including but not limited to: weight gain, ophthalmologic disorders, suicidal behavior and ideation, angioedema, hypersensitivity, abrupt or rapid discontinuation, abuse potential, congestive heart failure, renal failure, and creatine kinase elevations. Given the totality of clinical and nonclinical data, the current risk management approach appropriately safeguards subject safety, and the risk/benefit assessment is deemed positive.

In patients with moderate to severe renal impairment, sufficient efficacy of DS-5565 and acceptable risk of TEAEs on CNS are expected by the administration of the drug at an appropriate dosage based on the estimated exposure to the drug in those patients.

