### **9.8.5 Hospital Anxiety and Depression Scale**

At each visit, subjects will provide a self-assessment using the HADS. The HADS consists of 7 items to score depression (4-point scale) and 7 items to score anxiety (4-point scale). The subject will respond to each item on the questionnaire. Based on the results, the investigator will check for the presence or absence of depression and/or anxiety. If the subject is judged to have an AE, appropriate measures will be implemented such as referring the subject to a specialist. Results will be recorded in the CRF.

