### **11.7.2 Clinical Laboratory Evaluation Analyses**

For the hematology and blood chemistry test parameters, summary statistics will be calculated for the measured values and change from baseline at each scheduled visit. A shift table will be created based on the categories of “abnormal low”, “normal”, and “abnormal high” between baseline and each scheduled visit.

Additionally, for ALT, AST, T-Bil, and ALP, the number and percentage of subjects who meet the criteria specified in FDA Drug-Induced Liver Injury guideline and evaluation of drug-induced serious hepatotoxicity plot will be provided. For the urinalysis parameters excepting specific gravity, the number and percentage of subjects will be provided at each visit. Summary statistics will be tabulated for the specific gravity. A shift table will be created based on the categories of “normal” and “abnormal” between baseline and each scheduled visit.

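### HADS is planned only as subscale levels at each visit, so the number of subjects who worsen from their own baseline is never tabulated

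*Combined protocol and SAP*

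**What the plan says.** Section 9 lists HADS among the safety endpoints, and safety and tolerability are the primary objective (section 2.1.1). Section 3.2.3 gives the purpose: "Assessments by HADS and C-SSRS were selected to evaluate the risk of anxiety, depression, or suicidal tendency". Section 9.8.5 sets the schedule: "At each visit, subjects will provide a self-assessment using the HADS". Table 17-1 confirms Visits 1 to 11 plus early termination, so every treated subject should have a pre-dose score at Visit 2.

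The analysis, in section 11.7.7, is one sentence: "The subscales of anxiety and depression for HADS will be summarized at each scheduled visit". The synopsis and section 11.2 add that summaries are by CrCL group. Section 11.2 sets the default statistics for quantitative data: mean, SD, median, minimum, maximum and number of observations.

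Other repeated measures are treated differently. For hematology and chemistry, section 11.7.2 says "summary statistics will be calculated for the measured values and change from baseline at each scheduled visit", followed by shift tables. For weight, section 11.7.5 says: "Summary statistics will be calculated for measured values and changes from baseline in body weight at each scheduled visit". Change is also named for vital signs (11.7.3), ADPS (11.5.2.1), SF-MPQ (11.5.2.3) and sleep interference (11.5.2.5).

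Section 9.8.5 also gives HADS a clinical use: "Based on the results, the investigator will check for the presence or absence of depression and/or anxiety". If an adverse event is judged present, measures such as specialist referral follow.

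**The concern.** A safety scale repeated in the same people is most informative when each person is compared with their own pre-dose value. Followed as written, section 11.7.7 gives a series of cross-sectional summaries and never makes that comparison. The question HADS was chosen to answer is whether some subjects become more anxious or depressed on treatment, and the table cannot answer it with a count.

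The setting makes this matter more. There is a single open-label arm, so no control group shows what average drift to expect. Section 1.3 names suicide and suicidal ideation among the notable events already seen with the drug. If pain relief or expectation lowered the average score, a reassuring mean could sit beside worsening in a few subjects, and a reader of the study report could not tell from the HADS table.

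**Working it through.** **Inputs from the protocol.** About 35 subjects (section 11.11); a Visit 2 score and up to nine later ones, Visits 3 to 11 (section 9.8.5, Table 17-1); the default statistics of section 11.2. There is no planned HADS figure to reproduce. The plan's one sample-size calculation, which leads to 35, is sound: 1 - 0.9^30 = 0.958 for at least one event at a 10% rate, rounded up to 35 for dropout with no rate stated.

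**Assumed inputs.** Every HADS score and change below. Items are taken as scored 0 to 3, which the protocol does not state, so a subscale runs from 0 to 7 × 3 = 21. The 35 subjects are pooled for illustration; the actual table is split by CrCL group, and the split is not given.

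**Step 1: can the visit table identify who worsened?** Take two subjects scoring 5 and 14 at Visit 2. In case A neither changes. In case B the first goes from 5 to 14 and the second from 14 to 5. At the later visit both cases give mean (5 + 14)/2 = 9.5, minimum 5, maximum 14, n = 2. One subject has worsened by 9 points in case B and none in case A, yet the tables are identical. The planned statistics therefore do not determine how many subjects worsened.

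**Step 2: can the mean improve while a minority worsens?** With 31 subjects improving by 1 point and 4 (11%) worsening by 6:

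(31 × (-1) + 4 × 6)/35 = (-31 + 24)/35 = -0.20.

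To vary this, let k of 35 worsen by 5 points and the rest improve by d points. Mean change = (5k - (35 - k)d)/35.

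- d = 1.5: k = 2 gives -1.13; k = 3, -0.94; k = 5, -0.57; k = 7, -0.20.
- d = 1.0: k = 3 gives -0.49; k = 5, -0.14; k = 7, +0.20.
- d = 2.0: k = 3 gives -1.40; k = 7, -0.60.

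The mean stops improving when k reaches 35d/(5 + d), which is 5.8 for d = 1.0, 8.1 for d = 1.5 and 10 for d = 2.0. Masking is possible over a wide range, but not without limit.

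**Step 3: what would departures do?** If 32 subjects score 5 and 3 score 14, the visit mean is (160 + 42)/35 = 5.77. If those three have no later score, the next mean is 160/32 = 5.00, a fall caused only by who remains. The same table would show the maximum dropping from 14 to 5 and n from 35 to 32, so a careful reader would see that high scorers had left.

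**Step 4: what each addition would show.** Change from Visit 2 in subjects with both values removes the artefact in Step 3: if the 32 who remain also scored 5 at Visit 2, their mean change is 0. It does not cure Step 2, because with everyone present the mean change is still -0.20; its maximum shows only the single largest worsening at that visit. The count of worsened subjects comes from the distribution of each subject's largest increase, which also keeps the three leavers if their last scores are counted.

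**Step 5: does the text supply this elsewhere?** Section 11.2 says which subjects enter a change-from-baseline analysis but does not assign one to HADS. The missing-data rule in section 11.2 is for weekly ADPS only. Early termination is grouped with Visit 10 in section 6.4 but has its own column in Table 17-1, so a summary by scheduled visit leaves it unclear where a withdrawing subject's last HADS score is counted.

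**The case against.** A reader might infer that individual worsening goes undetected. The documents do not support that.

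- Section 9.8.5 requires a per-subject check of HADS that can lead to an adverse event. Section 11.7.1 counts treatment-emergent events by preferred term, by CrCL group and overall. Aggravation of a pre-existing symptom is also an adverse event (section 9.1.1).
- A positive C-SSRS answer is an event of special interest (9.1.1), is reported within 24 hours (9.2), and appears in the C-SSRS tabulation (11.7.6).
- Minimum, maximum and n give some view of extremes and attrition, as Step 3 shows.
- Withdrawn subjects are asked, as far as they cooperate, to complete Visit 10 and Visit 11 assessments (4.2.3), and HADS is part of both.

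A reader might also infer that HADS means will drift down through selective dropout. That is an assumption. The protocol gives no HADS data, no dropout rate and no rule linking a rise in HADS to withdrawal. The C-SSRS withdrawal criterion in section 4.2.1 concerns suicidality, and those subjects are among the most visible in the study. Excluding major psychiatric disorder and recent suicidality (section 4.1.3) may also leave less room for average scores to fall.

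Finally, section 11.2 defers detail to a SAP, and the text available contains no separate SAP section on HADS. The missing analysis may be added there.

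All of this stands, and it limits the point. It does not remove it. The investigator check has no defined score or size of change, and its result is not itself planned for tabulation. The extremes do not show whether a high scorer was already high at Visit 2. The other repeated scores have change named in the protocol, so its absence for HADS is not explained by deferral alone.

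**Conclusion.** The concern holds in a limited form. As written, section 11.7.7 makes no within-subject comparison of HADS, and its table cannot give the number of subjects who worsened from their own baseline. That conclusion rests on the text and on Step 1, and needs no assumption about average improvement or dropout.

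That a mean can improve while a few worsen is arithmetic. Whether it would happen in this study is unknown: the -0.2 and every other HADS value above are assumed. The accurate description is that individual worsening is not quantified from HADS, not that it is hidden.

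Severity is minor to moderate. HADS is one descriptive scale within the primary safety objective, and no stopping rule or planned test uses it. The gap leaves the stated psychiatric risk to clinical judgement and event reporting when the data to count it are already collected.

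**What to change.** In section 11.7.7, or in the SAP, keep the visit summaries and add for each subscale, by CrCL group and overall:

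1. The change from Visit 2 at each visit, in subjects with both values, with the default statistics of section 11.2. State that Visit 2 is the HADS baseline.
2. The distribution of each subject's largest post-baseline increase, counting early-termination and Visit 11 scores. State how early-termination scores enter the visit tables.

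If increases are grouped into categories, fix and justify them before the analysis; the documents give no HADS threshold or size of change to draw on. These are tabulation categories only and change no clinical rule.

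The cost is slightly more tabulation from data already collected, with no new visits or assessments. The main drawback is that the largest of up to nine scores in an uncontrolled arm will show some worsening by chance, so it should be read beside the change at each visit and not as a rate of drug-induced anxiety or depression.
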